### **5.3.3. Study BCX7353-203**

Interim efficacy, safety, PK, PD, and PK/PD results are available for Parts 1 and 2 of this ongoing proof-of-concept Phase 2 study in subjects with HAE. As of the cut-off date of 19 May 2017, 51 subjects with HAE were randomized and had received up to 28 days of treatment with BCX7353 once daily; 18 subjects received BCX7353 350 mg, 6 subjects received BCX7353 250 mg, and 7 subjects received BCX7353 125 mg. In addition, 20 subjects with HAE had received placebo. Part 3 of the study is currently ongoing.

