**Figure 1: Estimated exposure-response relationship for C1INH (CSL830 and Cinryze)**

As outlined in Section 5.3.3, unblinded safety, PK, PD, and efficacy data are available through completion of dosing in Part 2 of the current study, including doses of 350 mg (n = 18), 250 mg (n = 6) and 125 mg (n = 7). HAE attack rates were reduced at all BCX7353 dose levels relative to placebo, with the greatest reduction observed at the 125 mg QD dose level. At all doses, the fold above EC50 was exceeded by greater than 2-3 x EC50 and the minimum target concentrations of 41 and 71 ng/mL were also consistently exceeded at doses ≥ 250 mg QD (Table 2). Taken together, this data suggests that lower target concentrations than originally anticipated (ie 4x EC50 or lower) may be efficacious. This trough concentration corresponded to kallikrein inhibition of approximately 40%. However, it should be noted that data at doses < 350 mg has been obtained from a very small population thus far; completion of Part 3 will approximately double the number of subjects receiving 125 and 250 mg and will provide efficacy and trough PK and PD data on a small number of subjects dosed 62.5 mg QD.

**Table 2. Preliminary BCX7353 Trough Concentrations Obtained in Study BCX7353-203 Through Part 2 and Relationship to Pre-defined Target Concentrations Proposed as Efficacious**

BCX7353 Dose	n	Mean (SD) trough [BCX7353] ng/mL	Mean (SD) trough EC 50 , x-fold	Mean (SD) x-fold over target of 71 ng/mL at trough	Mean (SD) x-fold over target of 41 ng/mL at trough
350 mg	17	177 (58.84)	19.0 (7.04)	2.51 (0.874)	4.34 (1.51)
250 mg	6	132 (38.74)	14.2 (5.18)	1.90 (0.704)	3.29 (1.22)
125 mg	7	42.8 (16.52)	4.63 (2.00)	0.61 (0.234)	1.06 (0.406)

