Part 4 will be implemented if the 62.5 mg dose is shown to be less efficacious than the higher doses and the 125 mg dose efficacy is not sustained through the completion of Part 3, in order to further define the dose-response relationship. A 175 mg dose is proposed for study in Part 4, based upon predictions for exposure and kallikrein inhibition that are intermediate between the 125 and 250 mg doses. Results of simulations based upon PK data at the 125 and 250 mg doses in the current study and in Study BCX7353-101, suggest that 93% of subjects dosed with 175 mg QD will have trough concentrations above 4 x EC50, in contrast to 70% for a 125 mg dose. A 175 mg QD dose is also predicted to inhibit kallikrein by 62%, approximately midway between 125 mg (42%) and 250 mg QD (76%).

As discussed in Section 5.4.1.1, a dose < 125 mg BCX7353 QD may be efficacious based upon the HAE attack rate observed at this dose level in Part 2 and given that concentrations sufficient to block kallikrein through a dosing interval are greater than that now thought to be minimally efficacious (2 to 3 x EC50 [18 ng/mL and 27 ng/mL]). A 62.5 mg QD dose is the only dose < 125 mg QD being evaluated in the ongoing Part 3 of the study. It is unlikely that this dose will provide target BCX7353 concentrations in a significant proportion of subjects treated with this dose (see Figure 2). Nevertheless, this concentration and efficacy threshold has not yet been established and given that only 6 subjects will be dosed with 62.5 mg QD in Part 3, additional subjects may need to be dosed with 62.5 mg QD in Part 4 to elucidate the benefit: risk profile of this dose level.

If the interim review indicates that Part 4 is not needed, it will not be conducted.

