#### **11.1.13. Pharmacokinetics**

All plasma samples for determination of BCX7353 concentrations will be analyzed using a validated liquid chromatography-mass spectroscopy assay. Instructions for collection, processing, storage, and shipment of PK samples will be provided to the clinical site in the laboratory manual. Samples may also be analyzed on an exploratory basis for possible BCX7353-metabolites.

On Day 14 serial blood samples will be drawn for PK analysis predose and at the following time points: 1, 2, 3, 4, 5, 6, 8, and 24 hours postdose. For the 24 hour postdose samples, subjects will return to the clinic and have the blood sample drawn prior to dosing on Day 15. On Day 29, a trough PK blood sample will be drawn.

However, if the subject is unable to provide serial PK samples on Day 14, only the predose sample (i.e., trough PK sample) will be obtained on Day 14 and steady state serial PK samples will be obtained on Day 28, with a 24-hour PK sample drawn at the scheduled visit on Day 29.

Within 6 hours postdose, an acceptable window around each PK draw is  $\pm 10$  minutes. After 6 hours, an acceptable window is  $\pm 20$  minutes. Predose samples should be drawn within 5 minutes of the next scheduled dosing time.

Plasma BCX7353 PK parameters will be calculated as applicable, including the following: maximum concentration ( $C_{max}$ ), time to  $C_{max}$  ( $T_{max}$ ), area under the concentration versus time curve (AUC), and 24 hour half-life ( $t_{1/2}$ ) in plasma.

Actual date and time of PK sample collection will be recorded in the eCRF. In addition, the site should verify that the time of last dose taken at home prior to the visit is documented in the diary.

The lab performing bioanalytical analysis will be provided the randomization scheme. Two samples will ordinarily be analyzed for subjects randomized to placebo: the 4 hour postdose sample on Day 14 and the trough at Day 29.

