#### 13.2. Deriving and Summarizing Pharmacokinetic Parameters

Steady-state BCX7353 (metabolites if measured) plasma PK parameters will be estimated over the sampling interval for each subject using noncompartmental analysis (Phoenix WinNonlin version 6.4 or later, Certara, LP). Steady-state BCX7353 PK parameters collected on Day 14 or Day 28 will be combined by treatment group for summary statistics. The PK population will be used for the evaluation of PK parameter data.

The PK parameters that may be estimated are listed below. Additional analyses may be conducted as appropriate.

Pharmacokinetic Parameter	Definition
$AUC_{\tau}$	Area under the plasma concentration versus time curve over the dosing interval ( $\tau$ ) (ie, 8 hours for q8h dosing)
$C_{av,ss}$	Average steady-state plasma drug concentration during multiple-dose administration
$C_{max}$	Maximum observed concentration of drug
$C_{\tau}$	Observed drug concentration at the end of the dosing interval ( $\tau$ )
$t_{1/2}$	Estimate of the terminal elimination half-life of the drug, calculated as $0.693/\lambda_z$
CL/F	Apparent oral clearance after administration of the drug calculated as $Dose/AUC_{\tau}$
$\lambda_z$	Terminal elimination rate constant, estimate by linear regression of the terminal elimination phase of the natural logarithm of concentration of drug versus time curve
$V_z/F$	Apparent volume of distribution of the drug
$T_{max}$	Time of $C_{max}$

For the calculation of individual PK parameters, all PK concentrations that are BQL will be set to zero except when an individual BQL value falls immediately between two quantifiable values, in which case it will be set to missing. Actual elapsed time from dosing will be used to estimate

all the individual plasma PK parameters.

The appropriateness of estimation of  $\lambda_z$  and  $\lambda_z$ -derived parameter estimates will depend on an accurate estimation of the terminal elimination phase of the analyte, based upon inspection of individual subject PK profiles.  $\lambda_z$  and  $\lambda_z$ -derived parameter estimates that are considered by the Clinical Pharmacologist at BioCryst to be unreliable may be excluded from the summary statistics. In general, a minimum of three time points in the terminal phase with unadjusted  $R^2 \geq 0.7$  will be required to report  $\lambda_z$ .

Plasma PK parameters, except  $T_{max}$ , will also be summarized based on log transformed data.

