Dose proportionality will be analyzed using a power model, and the slope and its 90% confidence interval will be estimated. A secondary assessment of dose proportionality will be made using log transformed dose normalized AUC and  $C_{max}$ , which will be analyzed by using an analysis of variance including terms for dose effects. Each dose will be compared with the 125mg dose on a pair-wise basis, with the ratio and its 90% confidence interval estimated.

The trough plasma BCX7353 concentrations obtained pre-dose or 24 hour post-dose on Days 14, 15, 28 and 29 (as applicable) will be plotted and summarized by treatment group. Achievement of steady-state will be assessed by calculating the 90% CI of the slope of the linear regression of Days 14-29 trough concentration versus Day for each treatment group.

The number and proportion of subjects with average plasma BCX7353 trough concentrations ( $C_{tau}$ ) above 4x and 8x kallikrein inhibition  $EC_{50}$  values (35.8 ng/mL and 71.6 ng/mL) will be summarized by treatment group.

For each subject, the percent of plasma BCX7353 trough concentrations ( $C_{tau}$ ) above 4x and 8x kallikrein inhibition  $EC_{50}$  will be derived and summarized by treatment group.

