## 14. PHARMACODYNAMIC ANALYSES

### 14.1. Kallikrein Inhibition, Cleaved HK Fragments, and C1 INH

On-treatment plasma kallikrein inhibition data (assessed with and without stimulation by ellagic acid) will be expressed as percent inhibition compared to subject baseline activity. Ex vivo plasma kallikrein activity will be listed by subject, treatment, day, and time and summarized separately by treatment, day, and time. Descriptive statistics will be reported. Mean and individual plasma kallikrein inhibition versus time profiles will be plotted by treatment group. Plasma kallikrein inhibition data from Day 14 or Day 28 will be combined by treatment group for analysis. The difference between each active treatment group vs placebo and between active doses in plasma kallikrein inhibition will be analyzed using a repeated measures analysis of variance with time, treatment and time by treatment as fixed effects. Subject will be fitted as a random effect in the model. The point estimates and corresponding 95% confidence interval (CI) for treatment differences will be calculated at each time point.

Cleaved HK fragments and C1 INH functional levels and absolute change from baseline will be summarized by treatment group. The HK end of treatment /Baseline ratio will also be listed and summarized by treatment group. The difference between each active treatment group and placebo and the pairwise difference between active doses in C1inh Change from baseline, cleaved HK change from baseline and HK end of treatment /Baseline ratio will be analyzed using ANOVA with treatment as fixed effects. Baseline value will be included as a covariate. The point estimates and corresponding 95% confidence interval (CI) for treatment differences will be calculated for each comparison.

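### The steady-state regression in SAP 13.2 has no subject term, so its 90% CI for the trough slope is too wide, and no rule says how to judge it (minor)

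*SAP*

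**What the plan says.** SAP section 13.2 plots and summarises the troughs "obtained pre-dose or 24 hour post-dose on Days 14, 15, 28 and 29 (as applicable"), then assesses steady state by "calculating the 90% CI of the slope of the linear regression of Days 14-29 trough concentration versus Day for each treatment group". It names no subject effect, no log scale and no criterion for deciding that steady state holds.

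Protocol section 11.1.13 makes these repeated measurements. A subject has troughs on Days 14 and 15, or on Day 14 only if serial sampling moves to Day 28. In addition, "On Day 29, a trough PK blood sample will be drawn". The usual set is therefore Days 14, 15 and 29, or Days 14, 28 and 29.

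For the repeated kallikrein data in SAP section 14.1 the plan is explicit: "Subject will be fitted as a random effect in the model". Section 13.2 has no such statement. It also says that steady-state "PK parameters collected on Day 14 or Day 28 will be combined by treatment group for summary statistics".

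**The concern.** The SAP does not say outright that subject is ignored. It does name a random subject effect in the next section, though, so a programmer following the text would fit one pooled regression per arm.

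Subjects in an arm are sampled on essentially the same days, so differences in level between subjects say almost nothing about the slope over time. A pooled fit still counts those differences as residual error. The slope estimate is hardly affected, but its standard error is too large.

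With no acceptance rule, the natural way to read the output is to call the profile flat when the interval includes zero. Under that reading, an inflated interval makes flatness easier to claim, and most easily in the smallest and most variable arms.

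**Working it through.** The documents give no CI width, power or error rate for this check, so there is no planned figure to reproduce.

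**Inputs from the documents**
- Trough mean (SD) in ng/mL, protocol Table 2: 350 mg 177 (58.84), CV 33.2%; 250 mg 132 (38.74), CV 29.3%; 125 mg 42.8 (16.52), CV 38.6%.
- Arm sizes through Part 2: "18 subjects received BCX7353 350 mg, 6 subjects received BCX7353 250 mg, and 7 subjects received BCX7353 125 mg". Part 3 plans about 20 subjects in a 1:3:3:3 ratio, which is six per active arm; "completion of Part 3 will approximately double the number of subjects receiving 125 and 250 mg". This gives n = 18 (350 mg), 6 + 6 = 12 (250 mg) and 7 + 6 = 13 (125 mg). For the lowest dose, "only 6 subjects will be dosed with 62.5 mg QD in Part 3".
- Effective half-life 41-75 h, protocol section 5.3.1.

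**Assumptions**
- Within-subject CV 10-25% (not in the documents).
- Table 2 SD read as total variation.
- CV of 38.6% borrowed from 125 mg for the 62.5 mg arm.
- A 20% linear rise over the 15 days from Day 14 to Day 29.
- Steady state accepted when the 90% CI includes zero (not in the SAP).

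**Interval width.** For Days 14, 15, 29 the mean day is 19.33, and Sxx = 5.33² + 4.33² + 9.67² = 140.67 per subject. Days 14, 28, 29 give the same value. Then:
- pooled SE = SD_total / √(n × 140.67)
- SE with a subject effect = SD_within / √(n × 140.67)
- width ratio ≈ SD_total / SD_within, apart from a small difference in the t quantiles.

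| Arm | n | Ratio at within CV 10% | 15% | 20% | 25% |
|---|---|---|---|---|---|
| 350 mg | 18 | 3.3 | 2.2 | 1.7 | 1.3 |
| 250 mg | 12 | 2.9 | 1.9 | 1.5 | 1.2 |
| 125 mg | 13 | 3.8 | 2.5 | 1.9 | 1.5 |

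The ranges are therefore 1.9-3.8 at 10-15% and 1.2-1.9 at 20-25%.

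**Half-width over 15 days, pooled.** For 125 mg: 15 × 1.687 × 0.386 / √(13 × 140.67) = 22.8% of the mean. The same formula gives 16.6% at 350 mg, 18.1% at 250 mg and 34.8% at 62.5 mg. A 20% rise lies outside the typical half-width in the two higher arms and inside it in the two lower ones.

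**Half-width with a subject effect**, within-subject CV 10-15%: 5.0-7.6% (350 mg), 6.3-9.4% (250 mg), 6.0-9.0% (125 mg), 9.3-13.9% (62.5 mg).

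**Simulation**
- With no drift and within-subject CV 10-25%, the pooled 90% interval covers zero in 94-100% of trials.
- With a true 20% rise, it still includes zero in the following shares of trials:

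| Arm | Share missed |
|---|---|
| 350 mg | 29-40% |
| 250 mg | 41-47% |
| 125 mg | 66-71% |
| 62.5 mg | 82-87% |

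- If within-subject scatter is held constant while between-subject spread grows with the trough, the shares are 27-35%, 39-44%, 65-73% and 82-89%, in the same order.
- In that variant, fitting subject cuts the misses to 0-3% at n = 12-18 and 5-25% at n = 6 for within-subject CV 10-15%. At 20-25% they are 6-33% and 45-58%.

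**Drift to expect.** The Day 14 pre-dose trough follows 13 daily doses. The fraction of steady state is 1 − 2^(−13×24/t½), which is 94.4% at 75 h and 99.5% at 41 h. The remaining rise is therefore about 0.5-6%.

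**The case against.** The strongest reply is that nothing in the plan turns on this regression. Combining Day 14 and Day 28 parameters, averaging a subject's troughs for target attainment, and the Days 8-28 effective dosing period are all fixed unconditionally. A Day 14-29 regression could not support Days 8-13 under any model. Protocol section 5.3.1 reports steady state 6 to 12 days after the first dose, and section 5.3.3.2 reports it by Day 14 at all dose levels in this trial. The SAP also plans individual trough plots, which show within-subject drift directly. All of this stands, and it sets the severity.

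The direction of harm also depends on a rule the SAP does not give. If the interval had to lie inside a margin, an over-wide interval would make steady state harder to conclude, not easier. That stands too, and it makes the missing rule part of the point.

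A reader might go further and infer that the check will accept a 20% drift in any arm, or cannot fail. The figures do not support this: at 350 and 250 mg such a rise would be missed in fewer than half of trials. Nor can a two- to four-fold inflation be stated as fact, because it needs a within-subject CV of roughly 7-19%, which the documents do not give.

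Accumulation is not the only possible source of drift. Protocol section 5.2.3 reports possible irreversible CYP3A inhibition, and most doses are taken at home. That is a reason to do the check properly, but it is not evidence that drift is present.

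**Conclusion.** The point holds as a minor correction. Read literally, the planned regression puts between-subject variance into the error of a within-subject slope, and its 90% CI is too wide in every arm for the within-subject CVs considered. The size depends on that CV, as tabulated.

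The loss of sensitivity to a 20% rise is clear at 125 and 62.5 mg and moderate at 350 and 250 mg, and only if inclusion of zero is the rule. The 62.5 mg figure also rests on a borrowed CV and on six subjects; the protocol's alternative Part 4 could add six more.

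The documents do not support a claim that steady state has been wrongly concluded or that any efficacy result is affected. Given the stated half-life, steady state by Day 14 is likely. The defect is that this check adds less evidence for it than the data could give, and that no standard is set for judging the result.

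**What to change.** In SAP section 13.2, replace the pooled regression with a linear mixed model of log trough concentration on Day with a random subject intercept, fitted by treatment group. Report the Day 29/Day 14 ratio with its 90% CI, and judge it against a limit set before unblinding for the final analysis, not by whether the interval includes zero. Where the arm is too small for the interval to fit within that limit, as may happen at 62.5 mg, say that the result is inconclusive.

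The cost is one or two sentences of SAP text and one model statement. No new samples, visits or data are needed.

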## 14. PHARMACODYNAMIC ANALYSES

### 14.1. Kallikrein Inhibition, Cleaved HK Fragments, and C1 INH

On-treatment plasma kallikrein inhibition data (assessed with and without stimulation by ellagic acid) will be expressed as percent inhibition compared to subject baseline activity. Ex vivo plasma kallikrein activity will be listed by subject, treatment, day, and time and summarized separately by treatment, day, and time. Descriptive statistics will be reported. Mean and individual plasma kallikrein inhibition versus time profiles will be plotted by treatment group. Plasma kallikrein inhibition data from Day 14 or Day 28 will be combined by treatment group for analysis. The difference between each active treatment group vs placebo and between active doses in plasma kallikrein inhibition will be analyzed using a repeated measures analysis of variance with time, treatment and time by treatment as fixed effects. Subject will be fitted as a random effect in the model. The point estimates and corresponding 95% confidence interval (CI) for treatment differences will be calculated at each time point.

Cleaved HK fragments and C1 INH functional levels and absolute change from baseline will be summarized by treatment group. The HK end of treatment /Baseline ratio will also be listed and summarized by treatment group. The difference between each active treatment group and placebo and the pairwise difference between active doses in C1inh Change from baseline, cleaved HK change from baseline and HK end of treatment /Baseline ratio will be analyzed using ANOVA with treatment as fixed effects. Baseline value will be included as a covariate. The point estimates and corresponding 95% confidence interval (CI) for treatment differences will be calculated for each comparison.

